9.5 Therapy and Safety Endpoint Variable Definitions

9.5.1 Prior and Concomitant Medication

A prior medication is defined as any non-study medication that started before the date of first dose of study drug.

Concomitant medication is defined as any non-study medication that:

- Started before the date of first dose of study drug and is ongoing throughout the study or ends on/after the date of first study medication administration.
- Started on/after the date of first dose of study drug and is ongoing or ends during the course of study medication.

The start/stop dates recorded in the CRF will be used to determine when a medication is considered prior-to or after first dose of study drug. A medication can be considered both prior and concomitant if it was started prior to the first dose of study drug and continues to be taken after the first dose of study medication.

Unresolved missing start dates will be handled as follows for determination of concomitance: partial dates will be imputed in such a way as to consider the non-study medication as prior and/or concomitant if it is possible that the missing information could lead to a prior and/or concomitant outcome.

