#### **4.3 Withdrawal and Removal of Subjects**

Subjects will be informed that they are free to withdraw from study treatment and/or the study at any time at their own request without prejudice to their future medical care, or that they may be withdrawn at any time at the discretion of the investigator or Sponsor for safety, nonadherence to protocol requirements, or administrative reasons (eg, termination of study by Sponsor). Subjects wishing to withdraw from study treatment will be strongly encouraged to continue in the study and have all scheduled study procedures performed.

A subject must be withdrawn from treatment for the following reasons:

- subject becomes pregnant
- A subject's study treatment will be discontinued if the investigator or Sponsor considers it in the subject's best interest to stop treatment, (eg, for safety or significant tolerability reasons such as an AE). Subjects who have one of the following AEs must be withdrawn from study treatment.
  - IOP of >21 mm Hg
  - nasal septal perforation
  - new onset or worsening of cataract

A subject may also be withdrawn from study treatment for the following reasons:

- lack of efficacy
- protocol violation

A subject may be withdrawn from the study for the following reasons:

- withdrawal of consent
- adverse event
- protocol violation that makes it unsafe for the subject to continue in the study
- termination of the study

- lost to follow up
- public health measure
- other

If a subject withdraws from the study after starting study treatment, appropriate follow-up must be conducted wherever possible.

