## 5.6 Concomitant Medication

All pre-study medications used within 1 month before Visit 1 (Screening) must be recorded in the CRF. For subjects with comorbid asthma or COPD, pre-study inhaled steroid (beclomethasone or equivalent) use within the 3 months before Visit 1 (Screening) must be recorded in the CRF.

Concomitant medications include all medications and other treatments taken by the subject during the study, including those treatments initiated prior to the start of the study. All concomitant medications must be recorded on the CRF.

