8.9 Concomitant Medications

Concomitant medications include all medications and other treatments taken by the subject during the study, including those treatments initiated prior to the start of the study. Specifically, concomitant medications are defined as non-study medications with a start date on or after the first dose of study medication inclusive. Medications that started prior to the first dose of study medication but continued during treatment will also be defined as concomitant. Further details regarding the definition of concomitant medications are provided in Section 9.5.1.

Concomitant medications will be coded using the World Health Organization (WHO) Drug Dictionary (WHODrug), Version December 2010 or later, and summarized descriptively by treatment group and drug class with subject counts.

Concomitant medications will be summarized by therapeutic class and preferred term for the Safety Analysis Dataset. For each subject, multiple records of the same concomitant medication will be counted only once within each therapeutic class and preferred term.

All concomitant medications will be provided in a listing for the placebo run-in period based on the Safety Analysis set and Enrolled Subjects set.

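### SAP 9.5.1 leaves a medication both started and stopped after the last dose of study drug neither prior nor concomitant, although SAP 8.9 and Protocol 5.6 count it

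*SAP*

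**What the plan says.** Three places define concomitant medication.

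- **Protocol 5.6:** "Concomitant medications include all medications and other treatments taken by the subject during the study". The period is the study, not the time on drug. SAP 8.9 opens with the same sentence.
- **SAP 8.9**, which specifies the tables, then becomes more specific: "concomitant medications are defined as non-study medications with a start date on or after the first dose of study medication inclusive". It adds medications begun earlier and continued into treatment. It sets no condition on the stop date. It closes the paragraph with a pointer: "Further details regarding the definition of concomitant medications are provided in Section 9.5.1".
- **SAP 9.5.1** gives two bullets. For medications begun before dosing: "Started before the date of first dose of study drug and is ongoing throughout the study or ends on/after the date of first study medication". For medications begun later: "Started on/after the date of first dose of study drug and is ongoing or ends during the course of study medication". It defines prior medication as anything started before the first dose.

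Follow-up off drug is planned. Protocol 4.3 says: "Subjects wishing to withdraw from study treatment will be strongly encouraged to continue in the study and have all scheduled study procedures performed". SAP 7.1.3 builds its treatment policy strategy for treatment discontinuation on this. The schedule of procedures collects concomitant medication at every visit and at the Week 16 and Week 20 contacts.

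**The concern.** The second bullet of 9.5.1 ties the stop date to the period of study medication. The other two definitions do not. A subject who stops drug early and stays in follow-up can take a short course of something that has both a start and a stop date after the last dose. Under 9.5.1 that record belongs to no category.

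Concomitant medication use is a named safety endpoint (Protocol 3.2.2, SAP 3.4.4), and SAP 8.9 tabulates it by treatment group. Because 8.9 sends the programmer to 9.5.1 for detail, the narrower rule could well be the one coded. The tables would then omit part of what subjects took after stopping drug, which is where treatment of the event that led to stopping may fall. The adverse event rule in SAP 9.5.2 has no such limit: any event with onset on or after the first dose is treatment-emergent. An event that starts off drug would therefore be tabulated while a completed course given for it would not.

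The listing in SAP 8.9 does not close the gap, because it is described for the placebo run-in period.

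**Working it through.** There is no plan figure to reproduce, because this is a classification rule. The check applies each definition to dated records.

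**Inputs.** The rules are those of SAP 9.5.1, SAP 8.9 and Protocol 5.6. The subject is illustrative and is an assumption: first dose Day 1, last dose Day 60, followed to Day 168 (24 × 7). The SAP does not define 'ongoing', so it is read two ways:

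- *literal*: no stop date recorded;
- *lenient*: still being taken at the last dose, or no stop date recorded.

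**Rules as coded.**

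- 9.5.1, start before Day 1: counts if there is no stop date or the stop is on or after Day 1.
- 9.5.1, start on or after Day 1: counts if ongoing, or if the stop falls in Days 1 to 60.
- 8.9: counts if the start is on or after Day 1, or if the medication began earlier and continued into treatment.
- Protocol 5.6: counts if taken at any time in Days 1 to 168.

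| Start day | Stop day | 9.5.1 literal | 9.5.1 lenient | SAP 8.9 | Protocol 5.6 |
|---|---|---|---|---|---|
| -10 | 100 | yes | yes | yes | yes |
| 20 | 30 | yes | yes | yes | yes |
| 55 | 70 | **no** | yes | yes | yes |
| 80 | 90 | **no** | **no** | yes | yes |
| 55 | none | yes | yes | yes | yes |
| 80 | none | yes | yes | yes | yes |

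**Reading the table.**

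1. The Day 80 to 90 course is excluded by 9.5.1 on either reading and included by the other two definitions. It started after Day 1, so it is not prior medication.
2. The Day 55 to 70 course is excluded only on the literal reading.
3. The first bullet of 9.5.1 has no upper limit on the stop date, so the Day -10 to 100 record is kept. The two bullets therefore treat a stop date after the last dose differently, and no reason is given.

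**Whether another rule rescues the record.** The imputation rule in 9.5.1 opens "Unresolved missing start dates will be handled as follows for determination of concomitance" and deals with missing or partial dates. It does nothing for a complete stop date that falls after the last dose.

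**Whether the difference was declared.** SAP section 11, on changes from the protocol, does not list it, and the SAP introduction states that there are no deviations from Amendment 6.0.

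**The case against.** The best reply is that the right rule is already in the plan. SAP 8.9 governs the tables, agrees with Protocol 5.6 and has no stop-date condition, and it cites 9.5.1 only for detail. Nothing gives 9.5.1 precedence. That stands as far as it goes: it cannot be shown that the narrower rule will be programmed. But nothing gives 8.9 precedence either, and the section it points to says something different. A programmer who follows the pointer gets the incomplete table.

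Three stronger readings are tempting, and the documents do not support them.

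- *All medication taken after stopping drug is lost.* It is not. Anything begun before the first dose is kept whatever its stop date, and so is anything with no stop date. A course that straddles the last dose depends on how 'ongoing' is read.
- *Steroid use off drug would escape the composite strategy for the co-primary endpoints.* SAP 7.1.2 and 7.1.3 define the intercurrent events without reference to 9.5.1 or to a concomitant flag, and item 3b of 7.1.3 expressly covers such use after treatment discontinuation. SAP 6.1.1 summarises and lists intercurrent events separately, and SAP 9.3.5 takes exacerbation dates from a dedicated CRF page. Systemic steroids given for CRS therefore have their own route to a display.
- *The size of the gap is the time off drug.* A subject who stops at Week 8 spends (24 - 8)/24 = 67% of the period off drug, but that describes time in an invented subject, not lost records.

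**Conclusion.** The inconsistency is real and minor. On either reading of 'ongoing', a medication both started and stopped after the last dose is neither prior nor concomitant under SAP 9.5.1; on the literal reading, so is one that straddles the last dose. SAP 8.9 and Protocol 5.6 include both.

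The consequence is limited to descriptive concomitant medication tables. It arises only if 9.5.1 is the rule programmed, and only for subjects who stop drug early and remain in the study. The number of records at stake cannot be derived, because the documents give neither the share of such subjects nor their medication use. No hypothesis test, error rate or power figure is touched.

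**What to change.** Bring the second bullet of SAP 9.5.1 into line with SAP 8.9 and Protocol 5.6 by removing the stop-date condition. Suggested wording: *any non-study medication whose start date lies between the first dose of double-blind study drug and the last study visit, whatever its stop date.* This also removes the need to define 'ongoing' in that bullet.

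Showing medications started after the last dose in a separate post-treatment block is optional; neither SAP 8.9 nor Protocol 5.6 calls for it.

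The cost is one SAP sentence and the matching line in the dataset specification. No new data are needed, since Protocol 5.6 already requires all concomitant medications to be recorded on the CRF.

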9.5.2 Treatment Emergent Adverse Events (TEAEs)

A treatment emergent adverse event (TEAE) is defined as an adverse event with onset date on or after the first dose of randomized study drug.

All reports of adverse events should include the severity and relationship to study drug that are determined by the investigators. In the event of missing information, the following rules will be applied for the adverse event summaries:

- AEs with missing onset dates will be included as treatment- emergent (unless end date is prior to the first dose date)
- AEs with missing severity will be counted as severe in severity
- AEs with missing relationship to study drug will be counted as related

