### 7.4.2 Nasal Examination

The nasal examination will be performed via nasoendoscopy; see [Section 6](#), Visit Schedule Summary, regarding completion of this assessment, including visit time windows. The sites will be provided with a nasal examination worksheet and a polyp grading sheet. A summary of the key safety assessments from the nasal examination is provided in [Attachment 3](#). Findings from the nasal examination worksheet that are deemed to be clinically significant by the Investigator will be recorded on the AE CRF beginning at Visit 1 (Screening).

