## 8 SAFETY MONITORING AND REPORTING

### 8.1 Adverse Events

An AE is any untoward medical occurrence associated with the use of an investigational product in humans, whether or not considered related to the investigational product. This includes any occurrence that was new in onset or aggravated in severity or frequency from the baseline condition.

In this study, symptoms of CRS are collected as part of the primary and secondary endpoints. Changes or worsening of symptoms of CRS should not be reported as AEs. All events that meet the definition of a SAE will be reported as SAEs, regardless of whether they are protocol-specific assessments.

Abnormal results of diagnostic procedures, including laboratory test abnormalities, or from the nasal examination are considered AEs if they result in:

- discontinuation from the study treatment or discontinuation from the study
- require treatment or any other therapeutic intervention
- require further diagnostic evaluation which confirms a clinical significant abnormality (excluding a repetition of the same procedure that rules out an abnormality)
- are associated with clinical signs or symptoms that would have a significant clinical impact, as determined by the investigator

Subjects are encouraged to report AEs spontaneously or in response to general, non-directed questioning. All non-serious AEs are to be followed until the subject completes the study or is lost to follow-up.

Timely, accurate, and complete reporting and analysis of safety information from clinical studies is crucial for the protection of subjects, is the responsibility of the investigators and the Sponsor, and is mandated by regulatory agencies worldwide.

Each AE is to be documented on the CRF with reference to intensity, date of occurrence, duration, frequency, treatment, action taken regarding study drug, and outcome. Furthermore, each AE is to be classified as being serious or non-serious. Additionally, the investigator has to assess whether the AE is drug related (adverse drug reaction) or not. Changes of AEs and dates of ending have to be documented on the CRF.

Surgical procedures, planned before enrollment of the subject in the study, are not considered AEs if the condition(s) was (were) known before study inclusion. In the latter case, the medical condition should be reported in the subject's medical history.

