For the purposes of this study, the period of observation for collection of AEs extends from the time the subject gives informed consent until completion of the end-of-study visit or an early termination visit. SAEs will be reported through 30 days after the last dose of study drug administration.

The maximum severity (intensity) of the AE will be categorized by the investigator as shown in [Table 6](#).

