### **9.9.1 Adverse Events (AEs)**

All reported AEs will be coded using the Medical Dictionary for Regulatory Activities (MedDRA) version 20 or higher. Treatment-emergent AEs (TEAEs) are defined as AEs with onset dates on or after the start of double-blind study drug. The incidence of TEAEs during the study period will be tabulated by treatment group and body system (or System Organ Class [SOC] and preferred term) overall, by severity, and by relationship to study drug using subject counts and percent. Those AEs with missing onset dates or missing severity will be included as treatment-emergent. If an AE is reported more than once during the double-blind study phase, the greatest severity and the worst-case attribution will be used for presentation in tables.

Deaths, SAEs, and AEs causing discontinuation of study participation and /or study treatment will be tabulated by treatment group with subject counts and percent. Adverse events for individual subjects will be listed, along with information regarding onset, duration, severity, and relationship to study drug.

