8.2 Adverse Events

All adverse events will be coded using the Medical Dictionary for Regulatory Activities (MedDRA) Version 21.0 or greater. Treatment emergent adverse events (TEAEs) are defined as adverse events with onset dates on or after the first dose of DB study drug. Further details regarding the definition of TEAEs are provided in Section 9.5.2.

All AE summaries will include total number of TEAEs and total number of subjects with TEAEs unless otherwise stated. The incidence of adverse events will be summarized using descriptive statistics by system organ class and preferred term. Subjects are counted only once in each system organ class category, and only once in each preferred term category. For the summaries by severity, subjects are counted at the greatest severity and will not have the number of events included. Additional summaries by severity will provide all adverse events for overall TEAEs and treatment related TEAEs.

An overall summary of adverse events will include number (%) of subjects with TEAEs (and number of AEs), treatment-related TEAEs, SAEs, severe TEAEs, TEAEs that resulted in treatment discontinuation, and fatal AEs; this overall AE summary will be presented for the Safety Analysis set.

Additionally, summaries will be presented for all TEAEs by system organ class and preferred term (overall and by severity). TEAEs determined by the investigator to be treatment-related (overall and by severity) will be summarized. Serious AEs will also be summarized. TEAEs causing permanent discontinuation from treatment will be summarized, and AEs resulting in death will be summarized.

A summary of adverse events that started during the placebo run-in period will be presented for both Safety Analysis set and the Enrolled Subjects set.

Listings for pre-treatment AEs, fatal AEs, serious AEs, and TEAEs leading to discontinuation will also be presented.

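### The treatment-emergent AE rule uses onset date alone, so a run-in AE kept as one record that worsens on double-blind drug would be left out of the TEAE displays

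*SAP*

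**What the plan says.** Three places define a TEAE, and they agree. SAP 9.5.2: a TEAE "is defined as an adverse event with onset date on or after the first dose of randomized study drug". SAP 8.2: TEAEs "are defined as adverse events with onset dates on or after the first dose of DB study drug". Protocol 9.9.1: TEAEs "are defined as AEs with onset dates on or after the start of double-blind study drug". None mentions worsening of an event already present. The missing-data rules in SAP 9.5.2 cover absent onset dates, severity and relationship, and nothing else.

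Protocol 8.1 is wider when it defines an AE: "This includes any occurrence that was new in onset or aggravated in severity or frequency from the baseline condition". The same section starts AE collection at informed consent, requires changes in an AE to be documented on the CRF, and on grading says: "The maximum severity (intensity) of the AE will be categorized by the investigator".

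SAP 8.2 gives AEs that began in the run-in a summary of their own and lists pre-treatment AEs separately.

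**The concern.** Every subject uses a placebo device for 7 to 21 days before the first double-blind dose (Protocol 2.5), and AEs are already being recorded. Local nasal effects such as epistaxis and septal ulceration are among the AEs reported most often with this product (Protocol 1.2). Such events can begin in the run-in and then get worse on active drug.

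A rule that looks only at onset date cannot see that worsening. At stake is the between-group description of local tolerability. If active drug aggravates such events more often than placebo does, the omitted events fall mainly in the active groups, and the TEAE tables show a smaller contrast than occurred.

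**Working it through.** The plan gives no figure to reproduce. The check is to follow one event through the rules.

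**Inputs**
- TEAE rule: onset on or after the first double-blind dose (Protocol 9.9.1; SAP 8.2, 9.5.2).
- AE definition: includes aggravation from baseline (Protocol 8.1).
- Recording: AEs from consent, changes documented on the CRF, maximum severity graded per AE (Protocol 8.1).
- Run-in: 7 to 21 days (Protocol 2.5).
- Planned group size: 111 (Protocol 9.1).

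**Constructed case.** A mild AE starts on Day -5, is still present at the first dose, and becomes severe on Day 30. Whether worsening extends the old record or opens a new one is not stated, so both are shown.

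| Display (SAP 8.2) | One record, onset Day -5 | New record, onset Day 30 |
|---|---|---|
| TEAEs by class and preferred term | not counted | counted |
| TEAEs by severity | not counted | counted as severe |
| Treatment-related TEAEs, if judged related | not counted | counted |
| TEAEs ending treatment (summary and listing), if it did | not counted | counted |
| Run-in summary and pre-treatment listing | included; record graded severe | included; record graded mild |
| SAE and fatal AE summaries | not restricted to TEAEs | not restricted to TEAEs |

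The same clinical course gives 0 TEAEs under one convention and 1 under the other. Under the single-record convention, a severity reached on drug is attached to a run-in event.

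**Size per event.** SAP 8.2 counts a subject once per preferred term. One omitted event therefore lowers that row by at most one subject: 1/111 = 0.0090, about 0.9 percentage points. The effect is zero if the subject has another TEAE under the same term. Under the single-record convention, the missing clause can only remove such events from the TEAE tables.

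**Discontinuations.** Protocol 9.9.1 tabulates AEs that end study participation or treatment, without limiting them to TEAEs. SAP 8.2 restricts its discontinuation summary and listing to TEAEs. A single-record run-in AE that worsened and ended treatment would fall under the protocol's table but not the SAP's.

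**Precedent within the SAP.** SAP 9.5.1 lets a medication that spans the first dose be both prior and concomitant. SAP 9.5.2 counts an AE with missing onset as treatment-emergent unless its end date precedes the first dose. Both lean towards inclusion; known worsening after dosing has no matching provision.

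**The case against.** The strongest reply is that Protocol 8.1 already solves the problem. If aggravation is itself an AE, and each AE has its own date of occurrence, worsening on drug is a new AE with an on-drug onset and meets the TEAE rule. The protocol says that changes go on the CRF, not on the same record, and CRF completion instructions are not among the documents. This stands as a possible reading, so the loss cannot be called certain. It does not remove the point: nothing requires a new record, grading by maximum severity fits a single record at least as well, and sites could differ.

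A second reply concerns the nasal examples. Screening findings reach the AE CRF only if judged clinically significant (Protocol 7.4.2). A minor erosion that becomes significant on drug is first recorded then and is a TEAE. Septal perforation, significant mucosal injury or ulceration, nasal candidiasis and more than one frank epistaxis in the month before screening are exclusions (Protocol 4.2). A separate bleed on drug has its own onset date. All of this stands and narrows the exposed group to run-in AEs already on the AE CRF and ongoing at first dose. The separate nasal examination summary (SAP 8.5) does not fully cover them, because examinations take place only at screening and Week 24/ET.

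Third, safety is descriptive, with no inference (Protocol 9.9). That limits the consequence, but these tables are still the main account of tolerability.

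**Conclusion.** The TEAE definition omits worsening, although the protocol's own AE definition includes it, and should be amended. The consequence is conditional: for each run-in AE that is held as one record and worsens on drug, up to one subject is lost from the affected TEAE rows, and an on-drug severity is attached to a run-in AE. How often this would happen is unknown.

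A reader might infer more than the documents support:
- **That on-drug events are always understated.** This holds only under single-record handling, which no section settles.
- **That every AE summary is affected.** The SAE and death summaries are not restricted to TEAEs.
- **That screening nasal findings which worsen are generally lost.** Most are not AEs until they become clinically significant.
- **That the lack of a cut-off after the last dose is an error.** Subjects who stop drug are encouraged to remain (Protocol 4.3), so off-drug time can be long: stopping on Day 42 and staying to Day 168 leaves 168 - 42 = 126 days, or 126/168 = 75%, off drug. But counting all events after the first dose is an accepted inclusive convention and removes no on-drug event. The AE tables are subject and event counts, so the exposure duration in SAP 9.1.1 is not their denominator. For completers' non-serious AEs the gap is near zero.

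**What to change.** In SAP 9.5.2 and 8.2, and in Protocol 9.9.1, define a TEAE as an AE with onset on or after the first double-blind dose, or an AE present before that dose that worsens in severity or becomes serious after it.

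Identify worsening from the AE changes that Protocol 8.1 requires on the CRF. Where the pre-dose severity or the date of change cannot be recovered, count an ongoing run-in AE as treatment-emergent if it led to discontinuation or became serious after the first dose.

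Cost: wording in three places and a check of whether the AE CRF holds dated or graded changes. The documents do not confirm that it does, so it should not be assumed that no further data are needed. TEAE counts would rise slightly.

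Optional and secondary:
- Reconcile the end of AE collection. Footnote i of the procedures schedule (Protocol, and SAP Table 3.1) ends it at completion of the double-blind treatment period or the early termination visit; Protocol 8.1 ends it at the end-of-study or early termination visit.
- Add one supportive on-treatment table for subjects who stop drug but stay in the study. The 30 days after last dose that the protocol already uses for SAE reporting is an available window. The whole-study table is not wrong as it stands and should remain.
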